### **7.2.2 Reporting of Pregnancy and Lactation to the Sponsor**

Although pregnancy and lactation are not considered adverse events, it is the responsibility of investigators or their designees to report any pregnancy or lactation in a subject (spontaneously reported to them) that occurs during the trial.

Pregnancies and lactations that occur after the consent form is signed but before treatment allocation/randomization must be reported by the investigator if they cause the subject to be

excluded from the trial, or are the result of a protocol-specified intervention, including but not limited to washout or discontinuation of usual therapy, diet, placebo treatment or a procedure. Pregnancies and lactations that occur from the time of treatment allocation/randomization through 14 days following cessation of Sponsor's product must be reported by the investigator. All reported pregnancies must be followed to the completion/termination of the pregnancy. Pregnancy outcomes of spontaneous abortion, missed abortion, benign hydatidiform mole, blighted ovum, fetal death, intrauterine death, miscarriage and stillbirth must be reported as serious events (Important Medical Events). If the pregnancy continues to term, the outcome (health of infant) must also be reported.

Such events must be reported within 24 hours to the Sponsor either by electronic media or paper. Electronic reporting procedures can be found in the EDC data entry guidelines. Paper reporting procedures can be found in the Investigator Trial File Binder (or equivalent).

### **7.2.3 Immediate Reporting of Adverse Events to the Sponsor**

#### **7.2.3.1 Serious Adverse Events**

A serious adverse event is any adverse event occurring at any dose or during any use of Sponsor's product that:

- Results in death;
- Is life threatening;
- Results in persistent or significant disability/incapacity;
- Results in or prolongs an existing inpatient hospitalization;
- Is a congenital anomaly/birth defect;
- Is an other important medical event.

**Note:** In addition to the above criteria, adverse events meeting either of the below criteria, although not serious per ICH definition, are reportable to the Sponsor in the same timeframe as SAEs to meet certain local requirements.

- Is a cancer;
- Is associated with an overdose.

Refer to [Table 4](#) for additional details regarding each of the above criteria.

For the time period beginning when the consent form is signed until treatment allocation/randomization, any serious adverse event, or follow up to a serious adverse event, including death due to any cause, that occurs to any subject must be reported within 24 hours to the Sponsor if it causes the subject to be excluded from the trial, or is the result of a protocol-specified intervention, including but not limited to washout or discontinuation of usual therapy, diet, placebo treatment or a procedure.

For the time period beginning at treatment allocation/randomization through 14 days following cessation of treatment, any serious adverse event, or follow up to a serious adverse event, including death due to any cause, whether or not related to the Sponsor's product, must be reported within 24 hours to the Sponsor either by electronic media or paper. Electronic reporting procedures can be found in the EDC data entry guidelines. Paper reporting procedures can be found in the Investigator Trial File Binder (or equivalent).

Additionally, any serious adverse event, considered by an investigator who is a qualified physician to be related to the Sponsor's product that is brought to the attention of the investigator at any time outside of the time period specified in the previous paragraph also must be reported immediately to the Sponsor.

All subjects with serious adverse events must be followed up for outcome.

### **7.2.3.2 Events of Clinical Interest**

Selected non-serious and serious adverse events are also known as Events of Clinical Interest (ECI) and must be reported to the Sponsor.

For the time period beginning when the consent form is signed until treatment allocation/randomization, any ECI, or follow up to an ECI, that occurs to any subject must be reported within 24 hours to the Sponsor if it causes the subject to be excluded from the trial, or is the result of a protocol-specified intervention, including but not limited to washout or discontinuation of usual therapy, diet, placebo treatment or a procedure.

For the time period beginning at treatment allocation/randomization through 14 days following cessation of treatment, any ECI, or follow up to an ECI, whether or not related to the Sponsor's product, must be reported within 24 hours to the Sponsor, either by electronic media or paper. Electronic reporting procedures can be found in the EDC data entry guidelines. Paper reporting procedures can be found in the Investigator Trial File Binder (or equivalent).

Events of clinical interest for this trial include:

1. an elevated AST or ALT lab value that is greater than or equal to 3X the upper limit of normal and an elevated total bilirubin lab value that is greater than or equal to 2X the upper limit of normal and, at the same time, an alkaline phosphatase lab value that is less than 2X the upper limit of normal, as determined by way of protocol-specified laboratory testing or unscheduled laboratory testing.\*

\*Note: These criteria are based upon available regulatory guidance documents. The purpose of the criteria is to specify a threshold of abnormal hepatic tests that may require an additional evaluation for an underlying etiology. The trial site guidance for assessment and follow up of these criteria can be found in the Investigator Trial File Binder (or equivalent).

2. a confirmed (ie, verified by repeat testing) elevated AST or ALT laboratory value that is greater than or equal to  $5 \times$  ULN as a result of within-protocol-specific testing or unscheduled testing.

### **7.2.4 Evaluating Adverse Events**

An investigator who is a qualified physician will evaluate all adverse events with respect to the elements outlined in [Table 4](#). The investigator's assessment of causality is required for each adverse event. Refer to [Table 4](#) for instructions in evaluating adverse events.

Table 4 Evaluating Adverse Events

Maximum Intensity	Mild	awareness of sign or symptom, but easily tolerated (for pediatric trials, awareness of symptom, but easily tolerated)
	Moderate	discomfort enough to cause interference with usual activity (for pediatric trials, definitely acting like something is wrong)
	Severe	incapacitating with inability to work or do usual activity (for pediatric trials, extremely distressed or unable to do usual activities)
Seriousness	A serious adverse event (AE) is any adverse event occurring at any dose or during any use of Sponsor's product that:	
	† Results in death ; or	
	† Is life threatening ; or places the subject, in the view of the investigator, at immediate risk of death from the event as it occurred [Note: This does not include an adverse event that, had it occurred in a more severe form, might have caused death.]; or	
	† Results in a persistent or significant disability/incapacity (substantial disruption of one's ability to conduct normal life functions); or	
	† Results in or prolongs an existing inpatient hospitalization (hospitalization is defined as an inpatient admission, regardless of length of stay, even if the hospitalization is a precautionary measure for continued observation. (Note: Hospitalization for an elective procedure to treat a pre-existing condition that has not worsened is not a serious adverse event. A pre-existing condition is a clinical condition that is diagnosed prior to the use of a Merck product and is documented in the patient's medical history.); or	
	† Is a congenital anomaly/birth defect (in offspring of subject taking the product regardless of time to diagnosis); or	
	Is a cancer (although not serious per ICH definition, is reportable to the Sponsor within 24 hours to meet certain local requirements); or	
	Overdose, although not serious per ICH definition, whether accidental or intentional, with or without an accompanying adverse event/serious adverse event, is reportable to the Sponsor within 24 hours to meet certain local requirements.	
Other important medical events that may not result in death, not be life threatening, or not require hospitalization may be considered a serious adverse event when, based upon appropriate medical judgment, the event may jeopardize the subject and may require medical or surgical intervention to prevent one of the outcomes listed previously (designated above by a †).		
Duration	Record the start and stop dates of the adverse event. If less than 1 day, indicate the appropriate length of time and units	
Action taken	Did the adverse event cause the Sponsor's product to be discontinued?	
Relationship to Sponsor's Product	Did the Sponsor's product cause the adverse event? The determination of the likelihood that the Sponsor's product caused the adverse event will be provided by an investigator who is a qualified physician. The investigator's signed/dated initials on the source document or worksheet that supports the causality noted on the AE form, ensures that a medically qualified assessment of causality was done. This initialed document must be retained for the required regulatory time frame. The criteria below are intended as reference guidelines to assist the investigator in assessing the likelihood of a relationship between the test drug and the adverse event based upon the available information	
	The following components are to be used to assess the relationship between the Sponsor's product and the AE ; the greater the correlation with the components and their respective elements (in number and/or intensity), the more likely the Sponsor's product caused the adverse event:	
	Exposure	Is there evidence that the subject was actually exposed to the Sponsor's product such as: reliable history, acceptable compliance assessment (pill count, diary, etc.), expected pharmacologic effect, or measurement of drug/metabolite in bodily specimen?
	Time Course	Did the AE follow in a reasonable temporal sequence from administration of the Sponsor's product? Is the time of onset of the AE compatible with a drug-induced effect (applies to trials with investigational medicinal product)?
Likely Cause	Is the AE not reasonably explained by another etiology such as underlying disease, other drug(s)/vaccine(s), or other host or environmental factors	

Relationship to Sponsor's Product (continued)	The following components are to be used to assess the relationship between the Sponsor's product and the AE: (continued)	
	Dechallenge	Was the Sponsor's product discontinued or dose/exposure/frequency reduced? If yes, did the AE resolve or improve? If yes, this is a positive dechallenge. If no, this is a negative dechallenge. (Note: This criterion is not applicable if: (1) the AE resulted in death or permanent disability; (2) the AE resolved/improved despite continuation of the Sponsor's product; (3) the trial is a single-dose drug trial); or (4) Sponsor's product(s) is/are only used one time.)
	Rechallenge	Was the subject re-exposed to the Sponsor's product in this trial? If yes, did the AE recur or worsen? If yes, this is a positive rechallenge. If no, this is a negative rechallenge. (Note: This criterion is not applicable if: (1) the initial AE resulted in death or permanent disability, or (2) the trial is a single-dose drug trial); or (3) Sponsor's product(s) is/are used only one time.) NOTE: IF A RECHALLENGE IS PLANNED FOR AN ADVERSE EVENT WHICH WAS SERIOUS AND WHICH MAY HAVE BEEN CAUSED BY THE SPONSOR'S PRODUCT, OR IF RE-EXPOSURE TO THE SPONSOR'S PRODUCT POSES ADDITIONAL POTENTIAL SIGNIFICANT RISK TO THE SUBJECT THEN THE RECHALLENGE MUST BE APPROVED IN ADVANCE BY THE SPONSOR CLINICAL DIRECTOR AND THE INSTITUTIONAL REVIEW BOARD/INDEPENDENT ETHICS COMMITTEE.
	Consistency with Trial Treatment Profile	Is the clinical/pathological presentation of the AE consistent with previous knowledge regarding the Sponsor's product or drug class pharmacology or toxicology?
The assessment of relationship will be reported on the case report forms /worksheets by an investigator who is a qualified physician according to his/her best clinical judgment, including consideration of the above elements.		
Record one of the following:	Use the following scale of criteria as guidance (not all criteria must be present to be indicative of a Sponsor's product relationship).	
Yes, there is a reasonable possibility of Sponsor's product relationship.	There is evidence of exposure to the Sponsor's product. The temporal sequence of the AE onset relative to the administration of the Sponsor's product is reasonable. The AE is more likely explained by the Sponsor's product than by another cause.	
No, there is not a reasonable possibility of Sponsor's product relationship	Subject did not receive the Sponsor's product OR temporal sequence of the AE onset relative to administration of the Sponsor's product is not reasonable OR the AE is more likely explained by another cause than the Sponsor's product. (Also entered for a subject with overdose without an associated AE.)	

### 7.2.5 Sponsor Responsibility for Reporting Adverse Events

All Adverse Events will be reported to regulatory authorities, IRB/IECs and investigators in accordance with all applicable global laws and regulations, i.e., per ICH Topic E6 (R1) Guidelines for Good Clinical Practice.

## 8.0 STATISTICAL ANALYSIS PLAN

This section outlines the statistical analysis strategy and procedures for the study. If, after the study has begun, but prior to any final database lock, changes are made to primary and/or key secondary objectives, or the related statistical methods, then the protocol will be amended (consistent with ICH Guideline E9). Changes to exploratory or other nonconfirmatory analyses made after the protocol has been finalized, but prior to final database lock, will be documented in a supplemental Statistical Analysis Plan and referenced in the Clinical Study Report (CSR) for the study. Post hoc exploratory analyses will be clearly identified in the CSR. No separate Statistical Analysis Plan will be issued for this study.

### 8.1 Statistical Analysis Plan Summary

Key elements of the Statistical Analysis Plan are summarized below; the comprehensive plan is provided in Section 8.2 – Responsibility for Analyses/In-House Blinding through Section 8.9 – Sample Size and Power Calculations.

Study Design Overview	A Phase 1b, Open-label, Single-dose Study to Evaluate the Pharmacokinetics, Safety, and Tolerability of MK-7655A in Pediatric Subjects From Birth to Less Than 18 Years of Age With Confirmed or Suspected Gram-negative Infections
Treatment Assignment	Single IV dose of MK-7655A (IMI/REL)
Analysis Populations	Pharmacokinetics: Per Protocol: all subjects who comply with the protocol sufficiently to ensure that their data will be likely to exhibit the primary endpoints, according to the underlying scientific model, and who have at least 1 postdose PK data point. Safety: All Subjects as Treated (ASaT): All subjects who received infusion (including partial doses) of study medication.
Primary Endpoint(s)	Pharmacokinetic: Plasma PK concentration data; 4 PK samples per subject will be collected. Primary model-based endpoints for REL and imipenem and non-model-based endpoints for cilastatin are listed in Section 8.4.1 – Pharmacokinetic/Pharmacodynamic Endpoints.
Secondary Endpoints	Safety: Safety evaluation will be based on the following endpoints: AEs (including ECIs), local tolerability assessments, clinical laboratory data, vital sign measurements, and physical examinations findings.


Modeling and Simulation (M&S) Methods for Key Pharmacokinetic Analyses
	
Pediatric REL and imipenem data will be used to determine pediatric PK parameters by using the previous adult PK model as a starting point. The PK parameters will be continuously updated as pediatric PK data become available from each age cohort. A nonlinear mixed effects modeling approach will be applied for model building.
 
The target is <math>AUC_{0-\infty} \geq 37.5 \mu\text{M}\cdot\text{hr}</math> (and <math>\leq 200 \mu\text{M}\cdot\text{hr}</math>) for REL and <math>TMIC \geq 30\%</math> (and <math>AUC_{0-\infty} \leq 250 \mu\text{M}\cdot\text{hr}</math>) for imipenem. The goal of model-based simulations will be to derive a dosing regimen where these predefined targets are jointly achieved in a proportion of pediatric subjects similarly covered in adults (~90% probability of target attainment) for each age cohort.
 
For cilastatin, descriptive statistics will be provided for PK parameters by age cohort, based on NCA.
 
Details on modeling and simulation (M&S) methods are provided in Section 8.6.1 – Modeling & Simulation Methods for Pharmacokinetic Analyses.

Statistical Methods for Safety Analyses
	
Descriptive statistics will be provided for all safety assessments described above.

Interim Reviews
	
Interim reviews of PK and safety data are planned at 3 stages in the study. Dose modification may be suggested based on interim review results. The planned interim reviews are summarized in Section 8.7 – Interim Review for Potential Dose Adjustment.

Multiplicity
	
No multiplicity adjustment is planned.

Sample Size and Power
	
Based on PK Precision                  Proposed number of study participants by pediatric subset:  Cohort 1 (age 12 to <18 years); at least 6 subjects  Cohort 2 (6 to <12 years); at least 6 subjects  Cohort 3 (2 to <6 years); at least 6 subjects  Cohort 4 (3 months to <2 years); at least 8 subjects, at least 4 of whom are <1 year of age  Cohort 5 (birth to <3 months); at least 18 subjects with at least 6 younger neonates (<1 week age), at least 6 older neonates (1 to <4 weeks age), and at least 6 infants (4 weeks to <3 months)
 
Details on sample size calculation are provided in Section 8.9 – Sample Size and Power Calculations.

## 8.2 Responsibility for Analyses/In-House Blinding

The statistical analysis of the data obtained from this study will be the responsibility of the Clinical Biostatistics department of the Sponsor. The analyses and summaries described in Section 8.6.1 – Modeling & Simulation Methods for Pharmacokinetic Analyses are the responsibility of the Quantitative Pharmacology and Pharmacometrics group and the Early Clinical Development Statistics group of the Sponsor.

This trial is being conducted as a nonrandomized, open-label study (ie, subjects, investigators, and Sponsor personnel will be aware of subject treatment assignments after each subject is enrolled and treatment is assigned).

Subjects participating in this trial will be allocated to age cohorts as described in Section 2.1 – Trial Design. The Clinical Biostatistics department will generate the allocation schedule, and allocation/non-random assignment will be implemented in an IVRS or IWRS.

There are no plans to conduct formal interim analyses in this study. Planned interim reviews of PK and safety data for each age cohort are described in Section 8.7 – Interim Review for Potential Dose Adjustment. An internal M&S team will be appointed to review the PK profile and safety and tolerability data for each age cohort when PK data from 50% of subjects in each cohort is available. Dose modification may be suggested based on the results of interim reviews as described in Section 5.2.1.2 – Dose Modification.

### **8.3 Hypotheses/Estimation**

Objectives of the study are stated in Section 3.0 – Objective(s) and Hypothesis(es). No hypothesis testing will be performed for this study.

### **8.4 Analysis Endpoints**

#### **8.4.1 Pharmacokinetic/Pharmacodynamic Endpoints**

Plasma concentrations of REL, imipenem, and cilastatin will be determined. The REL and imipenem data will be used to develop a pediatric population PK model, which will be used to perform simulations to derive suitable pediatric doses. Cilastatin data will be used to summarize its PK profile based on NCA.

For REL, plasma exposure ( $AUC_{0-\infty}$ ) and  $C_{max}$  will be the primary endpoints. For imipenem, %TMIC, plasma exposure ( $AUC_{0-\infty}$ ), and  $C_{max}$  will be the primary endpoints. In addition, the following model-based population mean PK parameters for both REL and imipenem will be determined: CL and  $V_c$ .

For cilastatin, the following PK parameters will be determined:  $AUC_{0-\infty}$ ,  $C_{EOI}$ ,  $t_{1/2}$ , CL, and  $V_{ss}$ .

#### **8.4.2 Safety Endpoints**

A description of safety measures is contained in Section 7.0 – Trial Procedures. Safety assessments will include AEs, local tolerability assessments, clinical laboratory evaluations, vital sign measurements, and physical examinations.

### **8.5 Analysis Populations**

#### **8.5.1 Pharmacokinetics Population**

The Per Protocol population will be used for the PK analysis. This population is the set of data generated by the subset of subjects who comply with the protocol sufficiently to ensure that these data will be likely to exhibit the primary endpoints, according to the underlying scientific model. Compliance covers such considerations as exposure to treatment, availability of measurements, and absence of major protocol violations. Subjects with major protocol violations will be identified to the extent possible by individuals responsible for data

collection/compliance and its analysis and interpretation. Any subjects or data values excluded from analysis will be identified, along with their reasons for exclusion, in the CSR. At the end of the trial, all subjects who are compliant with the trial procedure as described and have at least 1 postdose PK data point available will be included in the primary PK analysis dataset.

### **8.5.2 Safety Analysis Populations**

The All Subjects as Treated (ASaT) population will be used for the analysis of safety data in this study. The ASaT population consists of all allocated subjects who received infusion (including partial doses) of study medication.

## **8.6 Statistical Methods**

### **8.6.1 Modeling & Simulation Methods for Pharmacokinetic Analyses**

Relebactam and imipenem data will be used to develop a pediatric population PK model by using previous adult data in the form of the adult population PK model, which will be continuously updated as pediatric PK data become available from each age cohort. Any missing postdose plasma concentrations will be treated as missing. Values below the limit of quantification will be assigned a value of zero. A nonlinear mixed effects modeling approach will be used for model building. A Modeling and Simulation Analysis Plan with further details on the methodology will be prepared and finalized before database lock and analysis of the data.

There will be no formal hypothesis testing. The target is  $AUC_{0-\infty} \geq 37.5 \mu\text{M}\cdot\text{hr}$  (and  $\leq 200 \mu\text{M}\cdot\text{hr}$ ) for REL and  $TMIC \geq 30\%$  (and  $AUC_{0-\infty} \leq 250 \mu\text{M}\cdot\text{hr}$ ) for imipenem. The goal of model-based simulations will be to derive a dosing regimen where these targets are jointly achieved in a proportion of pediatric subjects similarly covered in adults (~ 90% probability of target attainment) for each age cohort; hence, achieving these targets implies similar efficacy as that obtained in adults. An absolute (mg) or weight-based (mg/kg) dose, whichever is found most suitable for each age cohort, will be selected based on the simulation results.

For cilastatin, an NCA will be conducted to determine its PK parameters. Descriptive statistics will be provided for cilastatin PK parameters by age cohort.

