### **4.2.2.3 Rationale for Dose Interval and Trial Design**

A single IV dose of IMI/REL will be administered to each subject in this study. A single-dose rather than a multiple-dose study design was selected from the observed PK properties of IMI/REL in adults. A short half-life (approximately 30 to 60 minutes) of both imipenem and REL and lack of accumulation of any drug components was observed in adult studies; these properties are expected to be the same in pediatric subjects.

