#### Rationale for PK Sampling Scheme

Pharmacokinetic sampling will be conducted in each age cohort, taking into consideration the likely minimum body weight of each age cohort and recommended limits on pediatric blood sampling.

Four PK samples per subject will be collected in each of the age cohorts as follows:

1. First PK sample: predose sample taken within 30 minutes before the start of study drug infusion.
2. Second PK sample: collected within 10 minutes after the end of study drug infusion.
3. Third PK sample:
  - Cohorts 1 through 4: obtained 1.5 to 2.5 hours after the start of study drug infusion.
  - Cohort 5: obtained 2 to 5 hours after the start of study drug infusion.
4. Fourth PK sample:
  - Cohorts 1 through 4: obtained 4.5 to 6 hours after the start of study drug infusion.
  - Cohort 5: obtained 6 to 12 hours after the start of study drug infusion.

All PK samples must be drawn within the specified time windows, and the actual sampling times must be documented. The first PK sample establishes a baseline and will allow for evaluation of bioanalytical interference (ie, to ensure there is no analyte of interest detected before dosing). The second PK sample will be used to determine the maximum observed plasma concentration ( $C_{max}$ ). The third and fourth PK samples will provide data during the elimination phase of the study drug and thus, will allow characterization of the selected PK parameters,  $AUC_{0-\infty}$  and TMIC. For Cohort 5, a full PK profile is anticipated by the end of 6 hours; however, sampling out to 12 hours will provide additional information regarding the elimination tail. The above sampling scheme allows for a balance between the maximum coverage of the concentration profile across time required to adequately characterize the PK, while minimizing the number of blood samples per subject.

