updated regimen for the remaining subjects in Cohort 2. Therefore, the dosing regimen was changed to 15/7.5 mg/kg IMI/REL as a 60-minute intravenous infusion for the remaining Cohort 3 subjects.

After completion of enrollment of Cohorts 1 through 3 (2 to <18 years of age), the protocol-defined interim review of aggregate safety and PK data from these 3 cohorts was conducted. The observed safety data for all 19 subjects who received IMI/REL demonstrated an acceptable safety profile. PK data from the 18 PK evaluable subjects were used to develop a pediatric-specific population PK model for imipenem and relebactam. In order to extrapolate the developed pediatric population PK model for the older cohorts (2 to <18 years of age) to Cohorts 4 and 5 (<2 years of age), an adjustment function was included to account for a lack of full renal maturation for the subjects in this age range. Simulations were conducted to project the initial doses for Cohorts 4 and 5. The dosing regimen specified in Table 2 for Cohorts 4 and 5 was selected based on drug exposures that were projected to provide optimal probability of safety and efficacy.

For Cohort 4, simulations from the interim review showed that infusing IMI/REL at 15/7.5 mg/kg (rather than 10/5 mg/kg) over 60 minutes would result in projected efficacy and safety targets similar to the evaluated initial Cohort 4 dose of 10/5 mg/kg. Furthermore, choosing a 15/7.5 mg/kg dose for the remaining 4 subjects enabled data collection over an expanded dosing range, and therefore supports population PK model optimization and future clinical use. Additionally, the 15/7.5 mg/kg dosing regimen of IMI/REL is consistent with the current PRIMAXIN®/TIENAM® (imipenem/cilastatin) dosing recommendations for pediatric patients, for which there is a long history of safe and efficacious use.

Figure 2 Dose Modifications for Cohorts 1, 2, 3, and 4 After Interim Reviews

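### Section 8.6.1 sets every value below the quantification limit to zero in the REL/imipenem population PK model; for postdose samples this can bias CL, Vc, AUC and target attainment

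*Combined protocol and SAP*

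**What the plan says.** Section 8.6.1 describes a nonlinear mixed-effects model for REL and imipenem that starts from the adult population model. Within that paragraph it states: "Values below the limit of quantification will be assigned a value of zero". The sentence just before it, on missing concentrations, is limited to postdose values. The one on values below the limit of quantification (BLQ) has no such limit. The protocol gives no LLOQ, residual error model, data transformation, censoring method or BLQ sensitivity analysis. A separate Modeling and Simulation Analysis Plan is promised with further detail.

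Three other places bear on how often a postdose value would be BLQ:

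- Section 4.2.2.3 reports "A short half-life (approximately 30 to 60 minutes) of both imipenem and REL" in adults and adds that "these properties are expected to be the same in pediatric subjects".
- The sampling rationale in Section 4.2.3.1 sets the fourth sample as "Cohorts 1 through 4: obtained 4.5 to 6 hours after the start of study drug infusion". It gives the late samples their role: "The third and fourth PK samples will provide data during the elimination phase of the study drug". For the youngest group it says "For Cohort 5, a full PK profile is anticipated by the end of 6 hours", yet that group's fourth sample is drawn at 6 to 12 hours.
- Section 5.2.1.2.1 notes that, below 2 years of age, "an adjustment function was included to account for a lack of full renal maturation for the subjects in this age range".

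**The concern.** A BLQ result means a concentration somewhere between zero and the LLOQ. For the predose sample, zero is a sensible value. After dosing, the model predicts a positive concentration at every time, and an exact zero tells the fit something untrue with full confidence.

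Each subject has three postdose samples, and only the third and fourth cover elimination. They inform CL and Vc and, through them, AUC and %TMIC (Section 8.4.1). Those parameters drive the simulations that seek about 90% joint target attainment in each cohort and the interim dose reviews. Section 8.6.1 takes reaching the targets to imply efficacy similar to that in adults, so attainment that reads too high is the error that matters most.

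**Working it through.** **The plan's own figures.** There is no stated LLOQ or BLQ share to reproduce. Section 8.9 claims more than 80% probability of the target precision from replicate simulations. The full adult-model inputs are not given, nor is the BLQ handling in those simulations, so that figure cannot be rerun and is not used here.

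**Step 1: how late the fourth sample is.** Fraction of the end-of-infusion concentration left = 2^(−(t − T_inf)/t½), with infusions of 0.5 or 1 h.

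- Cohorts 1–4, t½ = 1 h: (4.5 − 1)/1 = 3.5 to (6 − 0.5)/1 = 5.5 half-lives, leaving 8.8% to 2.2%.
- Cohorts 1–4, t½ = 0.5 h: (4.5 − 1)/0.5 = 7 to (6 − 0.5)/0.5 = 11 half-lives, leaving 0.78% to 0.05%.
- Cohort 5, 1 h infusion, t½ = 1 h: 5 to 11 half-lives, leaving 3.1% to 0.05%.

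**Step 2: BLQ share with between-subject variability.** The CVs come from Section 8.9 (imipenem CL 50%, Vc 75%; REL CL 40%, Vc 50%). Assumptions: one compartment, LLOQ at 0.05–3% of the median end-of-infusion concentration, 15% residual error. There were 400,000 simulated subjects per case.

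- Fourth samples, Cohorts 1–4: 7–43% BLQ at a 60-minute half-life, 37–83% at 30 minutes.
- Third samples, Cohorts 1–4: 0–4% and 1–18%.
- Fourth samples, Cohort 5: 29–76% at 60 minutes, 1–37% at an assumed 2–3 h to reflect renal immaturity.

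**Step 3: what a zero does in the likelihood.** Let f be the predicted concentration.

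- Proportional error, SD = b·f: the standardized residual is (0 − f)/(b·f) = −1/b for any f. With b = 0.20 this is −5 SD at every BLQ point. No positive prediction can fit, so b inflates and f is pushed toward zero.
- Combined error: the same once f is large against the additive SD.
- Additive error, SD = a: the residual is −f/a. With a at 5% of the end-of-infusion level and an LLOQ no higher than that, a true value below the LLOQ is within 1 SD of zero, so little harm follows.

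**Step 4: fits.** Settings: REL CVs, 60-minute infusion, three postdose samples in the Cohort 1–4 windows, 40 subjects, 12 data sets per row, combined error (20% plus LLOQ/5), and an AUC cut-off set so that true attainment is 90%. The LLOQ is a percentage of the typical end-of-infusion concentration. Entries are CL / Vc as multiples of truth, then AUC attainment.

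| t½ | LLOQ | 4th sample BLQ | Set to zero | Omitted (M1) | Left-censored (M3) |
|---|---|---|---|---|---|
| 60 min | 0.1% | 7.1% | 1.03 / 0.96, 89.0% | 1.01 / 0.97, 89.7% | 1.01 / 0.96, 90.0% |
| 60 min | 1% | 22.9% | 0.99 / 0.95, 91.9% | 1.00 / 1.02, 91.8% | 1.01 / 0.97, 90.4% |
| 60 min | 5% | 51.9% | 0.96 / 0.79, 95.1% | 0.96 / 1.06, 93.5% | 1.01 / 0.98, 91.2% |
| 30 min | 0.1% | 41.5% | 0.93 / 0.86, 95.2% | 0.99 / 1.06, 91.2% | 1.00 / 0.99, 89.3% |
| 30 min | 1% | 70.0% | 0.90 / 0.69, 96.8% | 1.02 / 1.03, 90.1% | 1.00 / 1.00, 90.4% |
| 30 min | 5% | 91.5% | 0.87 / 0.55, 98.1% | 0.96 / 1.11, 92.4% | 1.01 / 1.00, 90.5% |

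The Monte Carlo standard error of CL is 0.02–0.03. The CL shifts in the first three rows are therefore within noise or close to it; those in the last three are not.

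Other error models, zero rule: additive error gave CL 0.98–1.01, Vc 0.96–0.98 and attainment about 91%. Proportional error was unstable, with the residual SD estimated at 0.3–3.5 against a true 0.20.

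**Step 5: why attainment rises.** Take the row at 70.0% BLQ. The true SD of log CL is √ln(1 + 0.40²) = 0.385, so the 90% cut-off lies 1.282 × 0.385 = 0.494 above the mean log CL. With CL at 0.896 of truth (ln = −0.110), attainment is Φ((0.494 + 0.110)/0.385) = Φ(1.57) = 94%. The zero rule also shrank the estimated spread in CL to 0.274 (M3: 0.373), giving Φ(0.604/0.274) = Φ(2.20) = 99%. The mean over data sets was 96.8%. The half-life is proportional to Vc/CL: 0.687/0.896 = 0.77, or 23% too short. That is why %TMIC can be understated while AUC is overstated.

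**Step 6: fits at the planned size.** These used 26 subjects (Cohorts 1–4), 20 data sets per case, 15% proportional error plus an additive SD of 0.15 LLOQ, and a 6 h interval assumed for %TMIC.

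- Combined error: at BLQ shares of 19–31%, CL 0 to −2%, Vc −4 to −7%, AUC attainment 88–93%. At 41–47%, CL −3 to −6%, Vc −9 to −25%, AUC attainment 94–96%.
- Proportional error: CL bias reached −17% at 43% BLQ. AUC attainment rose from 95% to 100% and %TMIC attainment fell from 90% to 80%.
- M3 in all cases: CL 0 to +2%, Vc 0 to −3%, attainment 87–90%.

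A further 26-subject check at about 70% fourth-sample BLQ, under combined error, gave CL −15%, Vc −19% and attainment 97% (M3: −1%, +6%, 90%).

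**The case against.** The strongest reply is that the size is unknown. The LLOQ, error model, number of compartments and observed BLQ share are all absent, and with few BLQ values or additive error the rule does almost nothing. That stands, and it is why the claim is only that the rule can bias.

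Other points that stand in part:

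- The fits are not the planned analysis. They use one compartment and no adult information, exclude Cohort 5, tune the cut-offs to 90% and leave out joint attainment and the upper AUC limits. Starting from the adult model might damp the bias.
- CL and Vc were simulated as uncorrelated. At a 60-minute half-life and LLOQ 0.05–1%, an assumed correlation of 0.8 lowers the fourth-sample BLQ share from 6–29% to 0–13%. At 30 minutes the effect goes both ways.
- The Step 6 fits with 20 data sets used 9 subjects on 30-minute and 17 on 60-minute infusions, following Section 5.2.2. Section 5.2.1.2.1 keeps Cohort 1 at 30 minutes, which gives 12 and 14. Those sections must be reconciled. The check at about 70% BLQ used 12 and 14 and points the same way.
- The proportional-error failures would probably show in ordinary diagnostics, so they should not carry the argument.
- Section 5.2.1.2.1 says the scaled adult model described the Cohort 1–3 data well. That is reassuring about fit, but it reports no BLQ share and does not test estimation with zeros in the data.
- The promised modeling plan may add an error model or a sensitivity analysis. Nothing says it may replace a rule the protocol already fixes.
- Omitting BLQ values kept attainment at 89.7–93.5%, so M3 is not the only defensible choice.

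**Conclusion.** The concern holds. Section 8.6.1 fixes an unqualified rule that suits the predose sample and is wrong in principle for postdose samples in a mixed-effects model. Under combined error the harm is small below about 30% BLQ in the fourth sample. From about 40% upward, CL was 3–15% too low, Vc 9–45% too low, and AUC attainment read 94–98% against a true 90%. Under additive error it was negligible; under purely proportional error the fits broke down or were badly biased. On the protocol's own half-life, BLQ shares in the harmful range are plausible in Cohorts 1–4. They may be lower in Cohort 5 if renal immaturity lengthens the half-life. All sizes rest on an assumed LLOQ and error model and a one-compartment simulation with few replicates. This should be fixed before database lock; confidence in the size is moderate.

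**What to change.** Replace the sentence in Section 8.6.1 with wording such as:

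> Postdose REL and imipenem values below the LLOQ are treated as left-censored in the likelihood (M3). A sensitivity analysis omits them (M1). Predose values below the LLOQ are set to zero. The LLOQ and the observed share of values below it are reported by cohort and sample.

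State the residual error model in the Modeling and Simulation Analysis Plan. Give the BLQ rule for the cilastatin noncompartmental analysis separately, because the text does not say whether the zero rule applies there.

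The cost is a protocol amendment, since Section 8.0 says that if "changes are made to primary and/or key secondary objectives, or the related statistical methods, then the protocol will be amended", together with a matching entry in the modeling plan and somewhat longer run times. No new data are needed. The model is refitted on all cohorts at the final analysis in any case. If the zero rule was used for the model already built on the 18 evaluable subjects in Cohorts 1–3, that fit should be rerun and compared.
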